### **Intervention and Control Conditions**

The SEE Program is a six-month personalized glaucoma coaching program. The glaucoma coach goes over tailored education from a web-based application and uses MI-based counseling to help glaucoma patients identify their barriers to optimal medication adherence and explore potential solutions. Participants attend three in-person coaching sessions. The coach also gives between-session support through four phone calls, with two phone calls between the first and second session and one phone call after each following session. Participants can elect to receive any or none of the following alarms/reminders: an audible alarm, a visual alarm, a text message one hour after a dose of medication is missed or a text message one hour after a dose of medication is missed. (**Figure 1**) The control group received enhanced standard care, receiving three mailings of glaucoma educational materials from leading eye care institutions in parallel to the three in-person coaching sessions. Glaucoma medication adherence will be monitored electronically for all participants between the baseline visit and the exit visit six months later.

[figure not shown]

Figure 1. Schedule of SEE Trial visits for Intervention and Control arms; Primary Outcome Assessment at 6 months

**Intervention:** During the first in-person coaching session, the glaucoma coach uses a web-based application to generate tailored glaucoma educational materials and teach eye drop instillation. The education is tailored on the following variables: name, gender, race/ethnicity, type of glaucoma, glaucoma test results (visual field tests and optic nerve photographs), previous laser or incisional glaucoma surgeries, recommended glaucoma medications, physician's name, cell phone and internet usage, social support, and barriers to adherence. The application also generates MI-based counseling prompts to guide the conversation between the coach and

patient. The coach shows the patient the tailored audio-visual educational materials on a large tablet (9"x12") that can be enlarged as needed for patients who are visually impaired. Text is read aloud. Videos can be played at higher volumes to ensure patients can hear. During the session, the coach helps the patient identify barriers to optimal adherence and uses the person's strengths and motivations to guide potential solutions. Over the course of the counseling session, the coach helps the patient put together a list of questions to ask the doctor at the next visit. At the end of each session, the coach uses the web-application to create a written action plan of the next steps to integrate medication taking into the patient's daily routine. Patients receive adherence monitors and choose any or all of their preferred modalities for receiving reminders when a medication dose is missed: an alarm (light or sound) and/or an automated phone call or text message.

Between-session phone calls are tailored to the patient's current level of adherence and focus on problem solving issues that arise. Phone calls are made using Google Voice software allowing the glaucoma coach to use his/her cell phone to call patients from a Google Voice number. This program facilitates a recorded history of call and text conversations. During the second in-person session, patients will discuss their motivation to take care of their vision and what strengths they have that they can use to enact their plan, practice instilling eye drops, and go over their daily routine for eye drop use. In the third session, patients can choose what parts of the personalized glaucoma educational content they would like to review and discuss and trouble shoot any new barriers that may have arisen. (SEE website: <https://seeglaucoma.org>)

Coaches have two different notes sections in the application. One is to record information for themselves to remember about the participant. The other notes section is for the counselors to record any questions the participants have that would be good to ask their physician. The

counselor then prints out a list of questions for the participant to take to their upcoming physician visit.

Patients will receive approximately 160 minutes of counseling (120 minutes in-person and four 10-minute telephone calls). This is within the range of counseling time ( $106 \pm 92.4$  minutes) that achieved significant behavior change in a meta-analysis. The glaucoma coaches update the participants' ophthalmologist on their adherence and action plan. Participants can call their coach if questions arise.

**Control condition, enhanced standard care:** The purpose of the trial is to measure whether the SEE glaucoma counseling program improves glaucoma medication adherence compared to current practice. Therefore, we chose to use enhanced standard physician care as the comparator to control for the attention effect given by additional education without greatly changing the comparator group from what would currently be delivered in clinic. The enhanced standard care group will receive non-tailored educational content by mail from current gold standard providers (American Academy of Ophthalmology, National Eye Institute and Glaucoma Research Foundation) in three doses parallel to the three in-person coaching sessions.

**Sub-Study:** At the end of the six-month trial, we will ask all intervention participants if they would like to enroll in the twelve-month sub-study for continued medication adherence using their same adherence monitors. Participants will be reconsented for the sub-study and will receive incentives of \$10/month by gift card or check in the mail for medication monitoring along with a retention letter. No reminders will be set on the medication monitors during this twelve-month period and participants will have no contact with the study team except for a call as a reminder to charge monitors if needed.

Participants in the sub-study will be scheduled for a final exit visit at the end of this twelve-month period. During the final exit visit, participants will complete the same surveys as in the six-month exit visit, less the Satisfaction with SEE survey and have their IOP's measured by the study team. Participants will receive a \$25 incentive for the visit and \$15 to offset transportation costs.

## OUTCOMES

**Primary Outcome:** Six-Month Medication Schedule Adherence. Medication adherence will be measured objectively using electronic monitors with a bottle-in-bottle technique where all glaucoma medications are placed inside electronic pill bottles. When the bottle cap is removed, the time and date stamp is sent to our database. An adherent event is defined as using an eye drop medication within a specified time window of a dose on the previous day. For example, for an eye drop medication dosed once per day, an adherent event is defined as taking the medication within  $24 \pm 4$  hours of the previous day's dose. We include this time window because the biological efficacy of eye drop medications decline when not taken on time. We will compare the current day's doses to the previous day's corresponding doses, ensuring that opening a bottle multiple times prior to a clinic visit does not inflate the adherence metric. Adherence will be calculated as the proportion of doses taken on time divided by total doses prescribed over the six-month study period. For participants on more than one medication,

adherence will be first measured at the medication level and then aggregated to the person level by dividing the total number of doses of all medication(s) taken on time by the total number of doses prescribed. Our primary outcome is the mean adherence in the control and intervention groups. We will also assess the proportion of patients who are  $\geq 80\%$  adherent.

**Secondary Outcome:** Glaucoma-related Distress. Glaucoma-related distress, or the emotional distress participants experience related to having glaucoma, will be measured using the Diabetes Distress Scale adapted for glaucoma (Cronbach's  $\alpha = 0.93$ ). The Diabetes Distress Scale consists of 17 items with four subscales that measure emotional burden (5 items), physician-related distress (4 items), regimen-related distress (5 items), and diabetes-related interpersonal distress (3 items). In our pilot validation study of three items from the regimen-related distress and emotional burden subscales in a glaucoma population, we found a significant association of increased glaucoma-related distress with poor electronically monitored glaucoma medication adherence (adjusted  $\beta = -2.47$ , standard error (SE) = 0.61,  $p=0.0001$ ).

**Exploratory Outcome:** Intraocular Pressure (IOP). Change in IOP between the baseline and exit visit will be assessed. We will measure IOP in both arms using the iCare (Tiolat Oy, Helsinki, Finland), a method that does not require corneal anesthesia. The iCare has been shown to correlate well with gold standard IOP measurement by Goldmann applanation tonometry. We will obtain three reliable (assessed by iCare) measures of IOP at each study visit and use the median as the study visit IOP which will be recorded both in the REDCap database and in the electronic health record to communicate with the participants' ophthalmologist. IOP control greatly reduces vision loss from glaucoma and is used as a surrogate marker of glaucoma control in drug and device trials and in clinical practice. However, given the short duration of the SEE Program, we would expect this intervention to cause at most a small reduction in IOP from baseline to six months, even if diurnal measures of IOP or obtaining IOP at a set time were feasible, which is not the case. We are not powered to detect small changes in IOP. Assessing whether there is a trend toward lower IOP in intervention participants will inform future larger scale trials with a measure of IOP control as a primary outcome.

### **Statistical Analysis Plan**

We will perform intent-to-treat analysis of all randomized participants to evaluate our primary, secondary and exploratory outcomes. We will compare the primary outcome variable, mean adherence, between the two groups using ANOVA, blocking on clinic. We will also analyze the proportion of subjects achieving  $\geq 80\%$  adherence between the treatment group and control group, with the Cochran-Mantel-Haenszel Test for equality of proportions. We will use Student's t-test on post-trial, 12-month medication possession ratios to assess longer-term effects of the SEE Program compared to enhanced standard care.

Additionally, we will use pre-trial medication possession ratios in ANCOVA to investigate whether treatment effectiveness is steady across different levels of pre-trial adherence. We will conduct a sensitivity analysis to test mean adherence between the two groups with ANOVA, blocking on clinic. To investigate trends in adherence over time, we will calculate adherence monthly. Spaghetti plots will visualize trends within the treatment and control groups (linear, step, decaying effect, etc.). Linear regression will test for trends of adherence over time by treatment group.

For the secondary outcome of glaucoma related distress (GRD), we will score the scale according to the measure's documentation at the baseline and exit visits and calculate change. Descriptive statistics and plots will be generated to understand the distribution of scores and change, overall and stratified by treatment group and clinic. The exit GRD score will be regressed on treatment group, adjusted for baseline GRD and clinic.

For the exploratory IOP outcome, exit IOPs will be analyzed using measures from both eyes. The distribution of IOP and IOP change will be assessed with descriptive statistics and plots. The effect of treatment on IOP will be assessed with a linear mixed regression model, adjusting for baseline IOP and clinic, and controlling for the correlation between eyes of a subject with a random subject effect.

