**Specific Aim: 2 Identify moderators and mediators of SEE Program effectiveness.**

The primary moderator we will assess is income (below the federal poverty line or not). We will also assess whether race (African American or not) and sex (male or female) moderate (interact with) the effect of the SEE Program on medication adherence. The primary moderator of treatment effect (income) will be assessed with an interaction term added to a linear regression model of continuous medication adherence, adjusted for known confounders of adherence.

**Specific Aim 3: Optimize the SEE Program for clinical dissemination using a mixed-methods evaluation of barriers and facilitators to implementation.**

In Aim 3, we will gain an in-depth understanding of participant experience in the SEE Program and of health system key stakeholders’ opinions on barriers and facilitators to implementation. Together, Aims 2 and 3 will give us a quantitative and qualitative evaluation of the SEE Program that will enable future program optimization through improved tailoring, more efficient protocols and opportunities to streamline the intervention. At the completion of these Aims, we will have developed a tool kit of all training and intervention materials to guide dissemination efforts in implementing better self-management support to improve glaucoma outcomes.

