### Exclusion criteria:

Do not speak English

Have a diagnose serious mental illness (defined as schizophrenia, bipolar disorder, or a major depressive episode with psychotic features)

Diagnosed cognitive impairment

Do not instill their own eye drops

Had laser or incisional glaucoma surgery within the last 3 months or scheduled during the six-month study period

Prisoners

Active uveitis or ocular infection

Participated in pilot study

Unable to attend all study visits

\*We will recruit men and women equally. We will oversample African American patients to ensure at least 25% representation in the trial sample.

UM Study staff will become registered Henry Ford Health Systems volunteers. Henry Ford staff will become registered as UM volunteers. This will allow for staff to access clinic space and electronic health records at each institution.

At UM and HF, research associates will call potential participants and obtain verbal consent to give a survey assessing self-reported medication adherence to determine study eligibility. Self-reported medication adherence will be measured from a single question asking “Over the past month, what percentage of your drops do you think you took correctly?” Those who self-report <85% adherence will be invited to participate in the study. Research associates will schedule a baseline visit to complete the informed consent process, the baseline survey, measurement of intraocular pressure and measurement of visual acuity and visual fields if participants have not had a reliable test with the last year(HVF SITA 24-2, ≤20% fixation losses, ≤15% false positives).

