### **Sample Size Aim 1: Compare the efficacy of the SEE Program with enhanced standard care in improving glaucoma medication adherence.**

We conducted brief interviews with 25 glaucoma specialists from throughout the US to gauge expert opinion regarding clinically important effect size. Their average recommendation for difference of group proportions of good adherence was 18.5 percentage points (95% CI 15.6-

21.5). Their average recommendation for difference of group mean adherence was 17.7 percentage points (95% CI 14.6-20.8). Additionally, mean medication adherence increased by 20 percentage points in our SEE Program pilot study from 65.7% ( $\pm 10.3$ ) at baseline to 85.7% ( $\pm 11.8$ ) after the program. With 97 participants in each group, a t-test has 80% power to detect a difference of 8 percentage points in mean adherence between the two groups, if the within group standard deviation (SD) is 20 ( $0.40 \times 20 = 8$ ). In our preliminary data the SD was 18, but we anticipate and plan for a possibly more diverse study group (calculated using R 'pwr' package). Our glaucoma specialists were divided on the importance of clinically important effect size, so we plan to be adequately powered for both continuous and binary adherence measures. Their average recommendation for difference of group proportions of good adherence was 18.5 percentage points (95% CI 15.6-21.5). The proposed sample size (n=97 per group) provides 80% power (at two-sided  $\alpha=0.05$ ) for Pearson's Chi Square Test of Independence to find a difference of 20 percentage points for the proportion of patients attaining good ( $\geq 80\%$ ) adherence between the intervention and control groups.

For our secondary outcome, with this sample size, we can detect a 1.1-point difference in mean change in Glaucoma Related Distress (scale 6-18) between trial arms if the SD is 2.8, as it was in our preliminary data. For this sample size in our exploratory outcome, we can detect a 1.9 mmHg difference in mean change in IOP between trial arms if the SD is 4.6 mmHg, as it was in our preliminary data. Although we will make concerted efforts to maximize retention, we will prepare for up to a 20% loss to follow-up as was experienced in our preliminary study and will enroll 115 participants in each arm for a total of 230 participants.

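### The primary adherence comparison is valid but uses no baseline covariate; prespecifying screening self-report and entry regimen would give a low-cost, probably modest gain in precision

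*Combined protocol and SAP*

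**What the plan says.** The Statistical Analysis Plan states: "We will compare the primary outcome variable, mean adherence, between the two groups using ANOVA, blocking on clinic". No baseline variable is named for this test. Under Randomization, allocation is blocked and stratified by site only.

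Elsewhere the same section treats baseline values differently:

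- The exit distress score is regressed on arm with baseline distress and clinic in the model.
- The intraocular pressure model adjusts for baseline pressure and clinic.
- The pre-trial medication possession ratio enters an additional ANCOVA, whose stated purpose is to see whether the treatment effect is constant across levels of pre-trial adherence.
- A sensitivity analysis of mean adherence is then described, again as ANOVA blocked on clinic.

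Two candidate covariates can be fixed before randomisation. At the screening call (the text under Exclusion criteria) every candidate is asked "Over the past month, what percentage of your drops do you think you took correctly", and only those answering below 85% are invited. The prescribed regimen is needed for everyone, because the Primary Outcome section divides on-time doses by doses prescribed.

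For sample size, Aim 1 states "With 97 participants in each group, a t-test has 80% power to detect a difference of 8 percentage points in mean adherence", "if the within group standard deviation (SD) is 20".

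**The concern.** In a linear model, a prespecified baseline variable that predicts the outcome removes part of the residual variance and so narrows the interval for the treatment difference. Past adherence is a natural candidate predictor of later adherence. Regimen is another: each dose is scored against a time window set by the previous day's corresponding dose, so a participant on several daily doses has more windows to meet. Neither variable is handled in the stratification or in the primary model.

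The plan adjusts its secondary and exploratory models for baseline but not its primary one, and gives no reason. What is at stake is efficiency. The estimate is less precise than the data might allow, and a chance imbalance in these variables is carried as ordinary sampling error when part of it could be removed. Precision matters here because the sample size has no slack at its own 8-point target.

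**Working it through.** **Inputs.** From Sample Size Aim 1: 97 per arm, difference 8 points, SD 20. Two-sided alpha of 0.05 is stated for the binary comparison ("provides 80% power (at two-sided $\alpha=0.05$ ) for Pearson's Chi Square Test of Independence") and assumed here for the t-test. The share of outcome variance explained by the added covariates within arm and clinic (R²) is not in the documents, so it is an assumption shown as a range.

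**Step 1: the plan's own figure.** Standardised difference = 8/20 = 0.40. The normal approximation gives 99 per arm for 80% power; the exact noncentral t gives 99.1, so 100. At 97 per arm, exact power is 79.2% (79.6% by the normal approximation), and the difference detectable with 80% power is 8.09 points. The stated 97 and 80% are reproduced to within rounding.

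**Step 2: the effect of adjustment.** Residual SD = 20 × √(1 − R²). Standard error of the difference = residual SD × √(2/97). Power is from the noncentral t with the residual SD in place of 20. The two extra degrees of freedom are negligible among 194 participants.

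| Assumed R² | Residual SD | Standard error | Power at 8 points | Detectable difference |
|---|---|---|---|---|
| 0 (as planned) | 20.00 | 2.87 | 79.2% | 8.09 |
| 1% | 19.90 | 2.86 | 79.6% | 8.05 |
| 4% | 19.60 | 2.81 | 80.8% | 7.92 |
| 10% | 18.97 | 2.72 | 83.2% | 7.67 |
| 16% | 18.33 | 2.63 | 85.6% | 7.41 |

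The equivalent increase in sample size is 1/(1 − R²): about 1%, 4%, 11% and 19%.

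**Step 3: why the lower rows deserve weight.** Entry truncates self-report below 85%, which weakens its correlation with any outcome. If the unrestricted correlation is r and screening leaves a fraction u of the SD, the restricted value is u·r / √(1 − r² + u²r²). With an assumed r = 0.4 and u = 0.5, 0.7 or 0.9, this gives 0.21, 0.29 or 0.37. The corresponding R² values for self-report alone are about 5%, 9% and 13%. A lower starting correlation gives less.

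**Step 4: with the planned attrition.** The plan says it will "prepare for up to a 20% loss to follow-up as was experienced in our preliminary study and will enroll 115 participants in each arm". A full 20% loss leaves 115 × 0.8 = 92 per arm, where unadjusted power is 77.0%. At R² of 1%, 4%, 10% and 16% it becomes 77.4%, 78.6%, 81.2% and 83.8%.

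**The case against.** The strongest reply is that nothing is wrong. The ANOVA matches the stratified design, is unbiased and keeps its type I error, and its confidence interval already allows for chance imbalance. All of that stands, so a reader should not infer that the planned test is biased or mistaken.

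Second, the gain may be negligible. No section links this one recall question, or the number of doses, to electronically monitored adherence. This also stands, and a reader should not infer gains at an R² of 20% or 30%, which nothing in the documents supports.

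Third, 8 points is what the sample can detect, not what the surveyed specialists thought important. Their average was 17.7 points (95% CI 14.6 to 20.8), and at 14.6 points the unadjusted test has 99.9% power with SD 20. The plan also reports that "In our preliminary data the SD was 18", at which power for 8 points is 86.9%. This limits the importance of the point for the power of the test. The interval would still be narrower with adjustment, and 8 points at SD 20 remains the plan's stated basis.

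Fourth, baseline adherence already appears through the possession-ratio ANCOVA. That is an additional analysis of whether the effect varies, and it does not change the primary test.

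Fifth, a reader might infer an internal contradiction, because the Aim 2 moderator model of the same outcome is "adjusted for known confounders of adherence". The documents do not support that. The confounders are not listed, so neither covariate can be said to be among them. Income, race and sex are also not randomised, so adjustment has a purpose there that it lacks for the randomised contrast.

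Finally, no baseline daily-dose variable is defined; the Primary Outcome section shows only that prescribed doses over six months are needed. This stands, and the fix must supply a definition.

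**Conclusion.** The point holds as a modest efficiency improvement of uncertain size. The primary analysis is sound as planned but leaves unused a baseline measure that every participant has before randomisation, in contrast to the plan's own distress and pressure models.

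At 97 per arm, the gain at 8 points runs from 0.4 percentage points of power (R² 1%) to 6.4 (85.6 − 79.2, R² 16%). These figures assume SD 20, two-sided alpha of 0.05, and R² values that the documents neither give nor exclude. If the covariates turn out to be weak, almost nothing is lost by including them.

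**What to change.** Before outcomes are seen by arm, amend the Statistical Analysis Plan so that:

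1. The primary test is a linear model of six-month adherence on arm, clinic, screening self-reported adherence (continuous) and number of prescribed daily doses at entry.
2. The dose covariate is the regimen fixed at randomisation, not the six-month denominator, which can change after allocation. Its definition should state how doses are counted (by eye or by bottle) and how combination drops are treated.
3. The adjusted mean difference is reported with its 95% CI.
4. The clinic-only ANOVA is kept as the sensitivity analysis. As worded, that analysis repeats the primary one, so this gives it a distinct role.
5. The possession-ratio ANCOVA stays as the separate look at whether the effect varies.

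The cost is SAP wording and one defined baseline variable. No new measurement of self-report, no refill data and no extra participants are needed.

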**Participant Assessments:** After eligibility has been confirmed and informed consent has been obtained, prior to randomization, a research associate will measure participants’ intraocular pressure (IOP), record socio-demographic characteristics, administer a baseline survey including measures of glaucoma-related distress, glaucoma knowledge, perceived competence, motivation, self-efficacy, and autonomy support from their eye care team. IOP measurements will be taken at all in-person study visits. Surveys will be administered by study staff on a tablet with the ability to enlarge the font or have the survey read out loud. Eye drop instillation will be video-recorded. Additionally, we will use commercially available inertial measurement unit sensors (Xsens-dot, Movella, Netherlands) to assess the kinematics of all eye drop instillations. The sensor will be attached to the bottom of the artificial tear by a custom made silicone sleeve and will not interfere with the dispensing of the artificial tears. Snellen visual acuity will be recorded on all participants. Humphrey visual field testing (SITA Fast, 24-2) will be performed on participants who have not had a reliable visual field (SITA, 24-2) within the last year. Participants will be randomized to the SEE Program (experimental) or enhanced standard care by the physician with additional written education materials (control). Medication adherence will be monitored electronically for all participants from baseline through the end of the 6-month program period. A baseline measure of medication adherence will be obtained by an objective method (medication possession ratios assessed from pharmacy refill data for six months prior to study participation) and subjective method (survey). After six-months, a research associate will video-record eye drop instillation, administer a survey with the same behavioral and psychosocial measures and a quantitative program evaluation, and then a masked research associate will measure IOP and conduct a 15-30 minute semi-structured interview with participants in the SEE Program arm to assess their experience with the program. Additionally, we will call participants that do or did not return for the exit visit to ask if they will complete the exit surveys over the phone. All data will be entered into the REDCap

---

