database. Following completion of the program, pharmacy refill data will be collected for an additional 12 months to assess longer-term effects of the SEE Program.

Randomization: After baseline testing, participants will be given their randomization assignment. We will use block randomization stratified by site to allocate participants to the intervention or control groups. A randomization list using blocks of varying sizes (2, 4, and 6) will be produced in TATUM for each site. Block randomization maintains approximate group size balance during the trial. Varying the block size lowers the likelihood of knowing the group assignment of the next eligible participant. Randomized group status will be available to the research associate by email after baseline information and consent are entered into REDCap and eligibility is confirmed.

Retention strategies: Participants receive incentives: \$25 for each completed study visit and \$10/month for six months for using the electronic adherence monitor during the trial. The coaching program will be delivered free of charge. Participants randomized to the control arm will have the opportunity to schedule a free coaching session after completing all follow-up assessments. Participants will be given \$15 to defray travel costs for each study visit. If a participant has no other means of transportation and lives within 10 miles of the clinic, transportation will be arranged instead of the travel reimbursement.

The research associates will make multiple attempts to re-schedule missed appointments within a one-month window. We will also employ a combination of retention strategies, including pre-appointment reminder calling, phone follow-up of missed appointments, updating of contact information at each visit, and distribution of materials with study phone numbers. Participants will receive a birthday card mailed to their address from the study team.

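### The 12-month possession-ratio comparison is an unadjusted t-test that leaves out the pre-trial ratio and the stratification site, giving up whatever precision they would add

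*Combined protocol and SAP*

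**What the plan says.** All references are to the combined protocol and SAP.

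- **Longer-term comparison (Statistical Analysis Plan).** A Student's "t-test on post-trial, 12-month medication possession ratios to assess longer-term effects of the SEE Program compared to enhanced standard care". No covariate or block is named.
- **Pre-trial ratio (Participant Assessments).** The objective baseline adherence measure is "medication possession ratios assessed from pharmacy refill data for six months prior to study participation". The same section has refill data collected for a further 12 months after the program.
- **Stratification (Randomization).** "We will use block randomization stratified by site to allocate participants to the intervention or control groups".
- **Other comparisons of arm means (Statistical Analysis Plan).** For the primary outcome: "We will compare the primary outcome variable, mean adherence, between the two groups using ANOVA, blocking on clinic". A sensitivity ANOVA also blocks on clinic. For distress: "The exit GRD score will be regressed on treatment group, adjusted for baseline GRD and clinic". For IOP, a "linear mixed regression model, adjusting for baseline IOP and clinic".
- **Stated analytic use of the pre-trial ratio (Statistical Analysis Plan).** "we will use pre-trial medication possession ratios in ANCOVA to investigate whether treatment effectiveness is steady across different levels of pre-trial adherence". The outcome of this ANCOVA is not named.

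**The concern.** Two pieces of information that may predict the 12-month ratio are in hand at randomisation: the same ratio measured beforehand, and the site within which patients were allocated. An analysis that ignores them leaves the variance they explain in the error term. If site matters, the t-test's standard error is also too large for a site-stratified allocation, which makes the test conservative.

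This is the plan's only randomised look at longer-term effect, because the 12-month monitored sub-study is offered to the intervention arm alone. What is at stake is a wider interval around that difference than the planned data require. The 12-month ratio is not listed as a primary, secondary or exploratory outcome, and the six-month primary analysis is untouched.

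**Working it through.** **Inputs.** From Sample Size Aim 1: 97 per arm, 80% power, difference 8 points, SD 20. Two-sided alpha 0.05 is stated there for the chi-square calculation and assumed for the t-test. These figures belong to the six-month outcome; no power is claimed for the 12-month ratio, so they serve only as a benchmark. Assumed, because the documents do not give them: the within-arm pre/post correlation r, the site difference D in SD units, and the fraction m of pre-trial ratios missing.

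**Step 1: reproduce the plan's figure.** The exact two-sample t-test with 97 per arm and 8/20 = 0.40 SD has 79.2% power (noncentral t, 192 df), against 80% stated. The difference detectable with exactly 80% power is 0.4043 SD.

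**Step 2: adjust for the pre-trial ratio, all ratios present.** Residual variance is multiplied by (1 − r²), so the detectable difference is 0.4043 × √(1 − r²). Power is for a true difference of 0.40 SD.

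| Assumed r | √(1 − r²) | Detectable difference (SD) | Power |
|---|---|---|---|
| 0 | 1.000 | 0.404 | 79.2% |
| 0.2 | 0.980 | 0.396 | 80.8% |
| 0.3 | 0.954 | 0.386 | 82.8% |
| 0.5 | 0.866 | 0.350 | 89.3% |
| 0.7 | 0.714 | 0.289 | 97.3% |

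The degrees of freedom spent on two covariates (192 down to 190) change the 0.4043 by less than 0.0001.

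**Step 3: adjust for site alone.** With a share p of patients at one site, site explains R² = p(1 − p)D² / (1 + p(1 − p)D²).

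- p = 0.5, D = 0.1: 0.0025/1.0025 = 0.25%, and 0.4043 × √0.9975 = 0.404 SD.
- p = 0.5, D = 0.5: 0.0625/1.0625 = 5.9%, and 0.4043 × √0.9412 = 0.392 SD.
- A 160/70 split, the most uneven that the enrolment cap allows with 230 in total, gives 0.2% to 5.0%, or 0.404 to 0.394 SD.

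**Step 4: missing pre-trial ratios.** A missing indicator that keeps everyone in gives 0.4043 × √(1 − (1 − m)r²). Dropping those participants leaves 97(1 − m) per arm. For m = 0.2 that is 77.6 per arm, with an unadjusted detectable difference of 0.4526 SD, then multiplied by √(1 − r²).

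| Assumed r | t-test, everyone | ANCOVA, m = 0.2, everyone kept | ANCOVA, m = 0.2, dropped |
|---|---|---|---|
| 0.3 | 0.404 | 0.389 | 0.432 |
| 0.5 | 0.404 | 0.362 | 0.392 |
| 0.7 | 0.404 | 0.315 | 0.323 |

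At r = 0.3, dropping 20% is worse than the t-test. Dropping 10% gives 0.407 SD, already no better than 0.404.

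**Step 5: error rate by simulation.** Site-stratified blocks of 2, 4 and 6 were simulated with 97 patients at each of two sites (194 in all), 6,000 trials per setting. Under the null the t-test rejected in 3.8% to 5.2% of trials. The lowest rate came at an assumed 15-point site difference with SD 20. ANCOVA on site and pre-trial ratio rejected in 4.8% to 5.6%. With r = 0 and no site difference, power for an 8-point difference was 79% for both methods, so adjusting costs essentially nothing if the covariates turn out uninformative.

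**The case against.** **It is only a preference.** The test is sound, the outcome is not a listed one, and the primary ANOVA also omits a baseline term. No figure in the documents establishes a gain. Low values of r are plausible: entry is restricted ("Those who self-report <85% adherence will be invited to participate in the study"), and the two windows differ in length, six months against twelve. At r = 0.3 or below the gain is at most 0.404 − 0.386 = 0.018 SD, and site alone moves the figure little. All of this stands as to weight. It does not remove the point: the change needs no new data, loses essentially nothing at r = 0, and could gain appreciably if r is higher.

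**The ANCOVA sentence may already cover it.** It comes straight after the t-test sentence and uses the pre-trial ratio. Its outcome is unnamed, so the 12-month ratio cannot be excluded. But it asks whether the effect is steady across levels of earlier adherence. That is a question of effect heterogeneity, and nothing presents it as the adjusted 12-month comparison. The ambiguity needs clearing up either way.

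**Stronger readings that the documents do not support.**

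- A reader might infer that the t-test is biased or inflates type I error. Under randomisation its arm difference is unbiased, and ignoring a prognostic stratification factor makes it conservative.
- A reader might infer that it departs from the whole SAP. The trend regression and the heterogeneity ANCOVA name no clinic term either. The contrast holds for the primary, sensitivity, distress and IOP comparisons of means.
- A reader might infer that adjustment would make the 12-month contrast a clean measure of lasting coaching effect. The intervention-only sub-study and the timing of the control arm's free coaching session are separate questions of interpretation. They are not part of this point, and ANCOVA would not resolve them.

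**Conclusion.** The point holds as a minor matter of efficiency, worth considering. The planned t-test is sound in the limited sense of type I error control and an unbiased arm difference. It forgoes precision of unknown size: nothing at r = 0, little at r of 0.3 or below (0.404 to 0.386 SD), and more at r of 0.5 (0.350) or 0.7 (0.289).

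The missing site term differs from the other comparisons of means but is worth little by itself. The missing baseline term matches the primary ANOVA and is simply an available improvement.

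These sizes rest on a borrowed 97 per arm and on assumed values of r, the site difference and the missing fraction. Confidence is high that both terms are absent from the text and only moderate that adding them would matter much.

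**What to change.** Replace the t-test sentence with an ANCOVA of the 12-month possession ratio on arm, site and pre-trial ratio. Pre-specify one rule that keeps participants without a pre-trial ratio in the analysis, either a missing indicator or simple imputation of the baseline covariate. State that the ANCOVA on steadiness of effect is a separate analysis, and name its outcome.

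The cost is a few sentences of SAP text. It needs no added visits, participants or data collection. Fixing the adjusted model in advance also removes any later choice between adjusted and unadjusted results.
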